3.0 ELIGIBILITY CRITERIA AND PARTICIPANT REGISTRATION

Inclusion Criteria:

- 3.1 Patients with confirmed or suspected malignant solid tumor of thoracic origin (e.g., lung, esophageal, thymus, mesothelioma, chest wall, mediastinum, trachea, pleura) with the intent to treat or biopsy by surgery as standard of care. Tumor must be ≥ 1.5 cm.
- 3.2 Patients with multicentric disease are eligible. Samples from all available tumors are requested for research purposes.
- 3.3 Patients with T2DM being treated with metformin (any dose) for a clinical indication at the time of study enrollment are eligible, and will continue metformin treatment as clinically indicated during the presurgical study period. Their dose of metformin will NOT be changed.

Patients not on metformin at the time of study entry must be willing to take metformin extended release (Glucophage® XR, 750 mg QD for 4 days, then 750 mg BID for 3-6 days) for a total of 7-10 days prior to surgery.

Patients do not require a diagnosis of diabetes to be enrolled in the study.

All patients must be willing to keep a drug diary indicating the dates and times of metformin administration.

One patient who has not been treated with metformin will be consented and enrolled. This patient will be asked to provide tumor, adipose, normal lung tissue, and blood samples, and all samples will be collected as described in section 4.2.2. These samples will be taken to serve as a control and are needed in order to optimize the metformin quantification.

- 3.4 Patients must meet the following clinical laboratory criteria:

- Absolute neutrophil count (ANC) $\geq 1,500/\text{mm}^3$ and platelet count $\geq 75,000/\text{mm}^3$.
- Total bilirubin $\leq 1.5 \times$ the upper limit of the normal range (ULN).
- Alanine aminotransferase (ALT) and aspartate aminotransferase (AST) $\leq 3 \times$ ULN.
- eGFR $> 60 \text{ mL/min}/1.73\text{m}^2$ or eCrCL $> 60 \text{ mL/min}$
- [name] Question For lung surgery do we need an INR < 1.6

- 3.5 Ability to give informed consent.

- 3.6 Patients must be willing to provide 20 mL of blood for research use.

- 3.7 Patient must be willing to provide consent for use of archived tissue for research.

Exclusion Criteria:

- 3.8 History of diabetes that is currently being treated without metformin.
- 3.9 Patients with a documented history of alcoholism, or binge drinking disorder.

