4.5 Analyses

1. *Pharmacokinetic analysis of metformin concentrations in plasma, whole blood, and tissues.*

The concentrations of metformin in all samples of blood, plasma, and tissue (tumor, normal, adipose) will be measured by a liquid chromatography (LC) with tandem mass

spectrometry (MS/MS) assay developed in the NCCC Clinical Pharmacology Shared Resource. The average value from the technical triplicates for each biological specimen will be used for calculations. This methodology is established in the NCCC Clinical Pharmacology Shared Resource for measurement of metformin concentrations in mouse tissues/tumors and cultured cells; this methodology will be re-optimized for analysis of human tissues using specimens collected from the single control subject enrolled in this study, in which specimens will be spiked with metformin to generate standard curves

In brief, the current assay consists of plasma protein precipitation using acetonitrile, and filtration over Phenomenex iPhree cartridges. The eluate is dried under nitrogen, resuspended in water, and injected into the LC-MS/MS. In mouse plasma (without full validation), assay accuracy was 91-98%, precision was <15% CV, and recovery was 89%.

2. *Immunohistochemical analysis of AMPK activity of pre- vs. post-metformin treated tumors.*

The goal of this exploratory endpoint is to determine whether metformin treatment alters phosphoprotein markers of AMPK activity in tissues.

In eligible patients, baseline (diagnostic biopsy specimen) and post-metformin (surgical specimen) tumor/normal tissue samples will be sectioned and processed for IHC in the NCCC Pathology Shared Resource. Tissue sections will be immunostained using antibodies against P-ACC(S79), and P-S6(S240/244). P-ACC and P-S6 will be scored using a Histoscore scale (36) that incorporates staining intensity and frequency. We expect metformin treatment to increase P-ACC and decrease P-S6 Histoscores, as metformin treatment should increase AMPK activity.

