8.0 STATISTICAL CONSIDERATIONS

8.1 PRIMARY ENDPOINT – Concentrations of metformin in tumor tissue.

8.2 SECONDARY ENDPOINT – Concentrations of metformin in adipose tissue, tumor-adjacent normal tissue, plasma, and whole blood.

8.3 EXPLORATORY ENDPOINT – Changes in AMPK activity induced by metformin, as determined by changes in P-ACC and P-S6 histoscores between pre- and post-metformin tissue specimens.

8.4 PRIMARY ANALYSIS PLAN – The primary analysis will measure the concentrations of metformin in biological triplicate samples of plasma, whole blood, and tissue specimens from each patient. Metformin concentrations will then be statistically analyzed to determine A) variability between biological triplicates, B) inter-individual variability between patients (within each tissue type; calculate descriptive statistics), and C) relationships between tissue types within each patient (compared by paired *t*-test or two-way ANOVA).

8.5 EXPLORATORY ANALYSIS PLAN – An exploratory analysis will determine whether metformin treatment significantly alters AMPK signaling in tumors compared to baseline. Histoscores from paired (pre- and post-metformin) tissue specimens will be compared by Wilcoxon rank sum test, and the correlation with metformin concentration will be established (the log transformation may be used to comply with the normal distribution assumption). Furthermore, an exploration of the metformin concentrations in plasma blood and tumor tissue and changes in tumor Histoscores will be undertaken using the direct PK-PD model (e.g., sigmoid Emax).

8.6 STATISTICAL TESTING - All statistical tests will be two-sided, and the overall type I error will be 0.05.

8.7 SAMPLE SIZE – We propose to evaluate 20 patients for the Primary Endpoint to account for the wide range (>75-fold) of steady-state plasma concentrations of metformin previously shown in

humans (12). There are no data on intra-tumor concentrations of metformin. As a surrogate, we will use plasma concentrations of metformin under the assumption that plasma and tumors will exhibit similar ranges of variability between patients. We will enroll one additional subject to acquire control tissues, bringing the total study accrual goal to 21 subjects.

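### Section 8.5 names the Wilcoxon rank sum test, an independent-samples test, for histoscores it calls paired; with positively correlated pairs this loses power

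*Combined protocol and SAP*

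**What the plan says.** Section 8.5 gives the only test of whether metformin changes AMPK signaling in tumors: "Histoscores from paired (pre- and post-metformin) tissue specimens will be compared by Wilcoxon rank sum test". The same section then plans a correlation with metformin concentration and a sigmoid Emax exploration, in which "changes in tumor Histoscores will be undertaken using the direct PK-PD model".

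Other sections confirm that the data are pairs:

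- Section 8.3 defines the exploratory endpoint as AMPK change "as determined by changes in P-ACC and P-S6 histoscores between pre- and post-metformin tissue specimens".
- Section 4.5, item 2, identifies the two members of each pair: "In eligible patients, baseline (diagnostic biopsy specimen) and post-metformin (surgical specimen) tumor/normal tissue samples will be sectioned".
- Section 8.4 names a paired t-test or two-way ANOVA for "relationships between tissue types within each patient", so the plan uses paired methods elsewhere.

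No section names a paired test for the histoscores. Section 8.6 makes all tests two-sided and sets the overall type I error at 0.05.

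**The concern.** The rank sum test pools the two sets of scores, ranks them, and refers the result to a null distribution that assumes independent samples. Two specimens from one patient are not independent in general. Under positive correlation, differences between patients largely cancel in the pre/post contrast, so its true variance is smaller than the test assumes. The p-value is then too large, the test rejects too rarely under the null, and it has less power than a paired test.

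At stake is a missed AMPK effect. Section 1.4 of the protocol treats the question of whether tumor concentrations are high enough to activate AMPK as one of the first steps in explaining inconsistent clinical results. A negative finding caused by the choice of test would bear on that question.

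A second point is for clarification only. Section 3.3 provides that "Patients with T2DM being treated with metformin (any dose) for a clinical indication at the time of study enrollment are eligible". A biopsy taken while a patient is on metformin is not a pre-metformin baseline. The wording in Sections 8.3 and 8.5 implies this, but no sentence says so for the test or for the Emax model of histoscore changes. Section 4.5 limits the staining to eligible patients without defining the term for this analysis.

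**Working it through.** **Plan's own figure.** There is none to reproduce: the plan states no power, effect size or correlation for this comparison.

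**Inputs from the documents.** Two-sided 0.05 (Section 8.6). At most 20 pairs, from the 20 patients in Section 8.7. Twenty is a ceiling, because Section 3.1 admits "Patients with confirmed or suspected malignant solid tumor of thoracic origin" and allows surgical biopsy, so some patients may have no earlier specimen.

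**Assumed.** Bivariate normal pre/post scores with unit SD; correlation rho of 0, 0.1, 0.3, 0.5 or 0.7; a shift of 0.6 SD for power; 20, 15 or 10 pairs.

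**Step 1: large-sample type I error of the rank sum test.** With Spearman correlation rho_S = (6/π)·arcsin(rho/2), the contrast variance shrinks by the factor (1 − rho_S), so

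size = 2·[1 − Φ(1.96/√(1 − rho_S))].

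This gives 5.0% at rho 0, 2.0% at 0.3, 0.6% at 0.5 and 0.05% at 0.7.

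**Step 2: what a paired test uses.** The within-patient difference has SD √(2(1 − rho)), so a 0.6-SD shift is a standardized difference of 0.6/√(2(1 − rho)): 0.6/1.414 = 0.42 at rho 0, 0.6/1.183 = 0.51 at rho 0.3, and 0.6/1 = 0.60 at rho 0.5. The signed-rank test gains from this; the rank sum test does not.

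**Step 3: simulation.** 20,000 trials per setting (Monte Carlo error at most about 0.7 points at 95%), comparing the asymptotic Mann-Whitney test with the exact signed-rank test.

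Type I error, 20 pairs:

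| rho | 0 | 0.1 | 0.3 | 0.5 | 0.7 |
|---|---|---|---|---|---|
| Rank sum | 5.0% | 4.0% | 2.4% | 0.8% | 0.1% |

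The signed-rank test stays at 4.8% to 5.0% throughout.

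Power at a 0.6-SD shift, rank sum v signed-rank (%):

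| Pairs | rho 0 | rho 0.1 | rho 0.3 | rho 0.5 | rho 0.7 |
|---|---|---|---|---|---|
| 20 | 44 v 43 | 42 v 44 | 43 v 56 | 42 v 70 | 42 v 89 |
| 15 | 33 v 31 | 32 v 35 | 30 v 43 | 28 v 56 | 26 v 78 |
| 10 | 22 v 22 | 21 v 24 | 19 v 29 | 16 v 38 | 13 v 57 |

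The loss at rho 0.3 is 13, 13 and 10 points for 20, 15 and 10 pairs. At rho 0.5 it is 28, 28 and 22 points.

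**Step 4: sensitivity.** A separate simulation with 20 pairs and other shifts gave the same pattern. At rho 0.5, power was 27% v 54% for 0.5 SD and 65% v 87% for 0.75 SD. With scores rounded to tens and clipped to 0–300 to create ties, rho 0.5 and a 0.5-SD shift, size was 0.7% v 4.8% and power again 27% v 54%. At rho −0.3 with 20 pairs, the rank sum size was 8.1%: under negative correlation the error runs the other way.

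**The case against.** The strongest reply is that this is a slip of one word. The sentence itself says paired, Section 8.3 speaks of changes, and Section 8.4 shows that the authors know paired tests, so signed-rank was probably meant. The power loss then occurs only if an analyst applies the named test literally. That reading is likely right, but the plan still prescribes the wrong test: following it loses power if the pairs are positively correlated, and correcting it silently departs from the plan.

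The comparison is also exploratory, no power was promised for it, and under positive correlation false positives fall rather than rise. All of that stands and limits the weight of the point.

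The size of the loss is wholly assumed. The correlation may be low: a biopsy and a surgical specimen are different samples, and Section 4.2.2 and Appendix A warn that delay before freezing affects phospho-proteins. This also stands. At rho 0 to 0.1 the loss is negligible, but the signed-rank test then costs almost nothing. The simulations test one marker at 0.05; if the overall 0.05 were shared between P-ACC and P-S6, the absolute powers would be lower for both tests.

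Finally, the question of metformin at biopsy is separate from the choice of test. The terms eligible, baseline and pre-metformin partly cover it. It is raised here only as a clarification, and the correction of the test does not depend on it.

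**Conclusion.** The concern holds. Section 8.5 assigns an independent-samples test to data it describes as paired, and nothing elsewhere corrects it. If the pairs are positively correlated, which is expected but not documented, the test is conservative and loses power: about 10 to 13 points at a correlation of 0.3 and 22 to 28 points at 0.5, for 10 to 20 pairs, normal scores and a 0.6-SD shift. Near zero correlation there is no material loss.

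The effect is confined to an exploratory comparison. The primary endpoint, the n=20 justification, the planned correlation with concentration and the Emax model do not depend on this test. It should be fixed because the error is definite and the correction is nearly free.

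**What to change.** In Section 8.5, replace the rank sum test with the Wilcoxon signed-rank test on within-patient differences (post minus pre).

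As a clarification, add a sentence such as: *Only patients not taking metformin at the diagnostic biopsy enter the pre/post comparison and any analysis of histoscore change, including the Emax model; patients on metformin at biopsy may contribute only to analyses of post-treatment histoscore against concentration.*

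Report the number of usable pairs. A Hodges-Lehmann median change with a 95% confidence interval is optional.

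The cost is two sentences in Section 8.5, with no added patients, specimens or assays and no effect on the primary endpoint or n=20. The clarification may leave fewer than 20 usable pairs.

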The log chi-square test is used to find the minimum detectable coefficient of variation [CV=relative standard deviation (SD)] for metformin in tumor tissues with $n=20$ sample size (number of tumors and patients). To compute the power of the test, we use the fact that the CV is approximately equal to SD on the log scale. Our one-sided power analysis implies that with $n=20$, under the null hypothesis that $CV=SD/\text{mean}=25\%$, the minimum detectable $CV=15\%$ with 90% power and the Type I error alpha=5%.

Based on the high number of patients undergoing surgical resection of lung tumors at DHMC, we project that this study will complete accrual within 24 months.

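### Section 8.6 promises two-sided tests and an overall type I error of 0.05, but the CV test in 8.7 is one-sided at the full 5%, and 8.4C and 8.5 add unadjusted tests

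*Combined protocol and SAP*

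**What the plan says.** - **8.6** covers every test without exception: "All statistical tests will be two-sided, and the overall type I error will be 0.05".
- **8.7** bases n=20 on a chi-square test of the tumor CV, with a null of 25% and a minimum detectable value of 15%. It begins "Our one-sided power analysis implies that with" n=20 and ends "with 90% power and the Type I error alpha=5" per cent. This test is not listed in the primary analysis plan (8.4), although the primary objective (2.1) carries the 25% limit.
- **8.4, item C** compares "relationships between tissue types within each patient" by a paired t-test or a two-way ANOVA. It lists no contrasts, gives no rule for choosing between the two methods and names no adjustment. Sections 8.1 and 8.2 name five matrices: tumor, adipose, adjacent normal tissue, plasma and whole blood.
- **8.5**, headed exploratory, adds tests on two markers (P-ACC and P-S6): "Histoscores from paired (pre- and post-metformin) tissue specimens will be compared by Wilcoxon rank sum test". It also adds a correlation with concentration.

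No section gives a hierarchy, an alpha split or a correction, or says which of these tests the 0.05 covers.

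**The concern.** There are two conflicts with 8.6.

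**Sidedness.** The only power figure in the plan comes from a one-sided test, while 8.6 makes every test two-sided. Both cannot hold, and the choice changes the power that n=20 delivers.

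**Overall error.** The CV test already uses the whole 0.05. Any further test under the same overall rate pushes the total above 5% unless something is adjusted. A reader who relies on 8.6 could take a tissue difference at p<0.05 as protected at 5% across the study, when nothing in the plan provides that protection. The contrasts and the method could also be chosen after the data are seen.

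**Working it through.** **1. Reproduce the figure in 8.7.** Inputs from 8.7: n=20 (19 df), null CV 25%, alternative 15%, one-sided alpha 5%, CV taken as the SD on the log scale.

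Reject if 19·s²/0.25² ≤ χ²(0.05; 19) = 10.117.

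Power = P(χ²₁₉ ≤ 10.117 × (0.25/0.15)²) = P(χ²₁₉ ≤ 10.117 × 2.778) = P(χ²₁₉ ≤ 28.10) = **91.9%**.

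With the exact log SD, √ln(1+CV²), power is 90.8%. The minimum detectable CV at 90% power is 0.25 × √(10.117/27.204) = 15.25%, where 27.204 is the 90% point of χ²₁₉. The stated 90% and 15% are therefore reproduced, one-sided.

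**2. The same test under 8.6 (two-sided 5%).** The lower critical value becomes χ²(0.025; 19) = 8.907.

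Power = P(χ²₁₉ ≤ 8.907 × 2.778) = P(χ²₁₉ ≤ 24.74) = **83.1%**. The upper tail adds a negligible amount. With the exact log SD, power is 81.4%.

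The minimum detectable CV is 0.25 × √(8.907/27.204) = **14.3%**. The smallest n with 90% power at CV 15% is **24**.

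**3. Family-wise error within 8.4C.** The plan does not fix the number of tests, so the common readings are shown. Simulation with n=20: log concentration = patient effect + independent patient-by-matrix error of equal variance (assumed), all matrices truly equal, unadjusted two-sided paired t-tests at 5%.

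| Reading of 8.4C | Contrasts | Family-wise error |
|---|---|---|
| Five matrices, tumor against each other matrix | 4 | about 16% |
| Five matrices, all pairs | 10 | about 30% |
| Tumor, normal, adipose: tumor against each | 2 | about 9% |
| Tumor, normal, adipose: all pairs | 3 | about 13% |
| One ANOVA F-test on patient means (five matrices) | 1 | about 5% |

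On the log scale these rates do not depend on the size of the variances.

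**4. Adding the CV test.** With the true tumor CV at the null boundary of 25%, where that test rejects 5% of the time, the chance of at least one false rejection is about **20%** (CV test plus four contrasts) or **33%** (CV test plus ten pairs). Above the boundary the CV test adds little: its rejection rate is 0.25% at a log SD of 0.32.

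**The case against.** The strongest reply is that this is a 20-patient, single-arm concentration study. Objectives 2.1 and 2.2 are to determine concentrations, no between-tissue hypothesis is stated, and 8.5 is already headed exploratory. One sentence limiting the 0.05 to a named test would settle the matter. That is largely right. It sets the weight of the point and the form of the fix. It does not make 8.6 correct as worded, since 8.6 exempts nothing and 8.4C sits in the primary analysis plan.

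The error rates also depend on assumptions. They fall where matrices truly differ, and the mouse data in 1.4 suggest that tumor and plasma may. They also move with the error structure. Plasma and whole blood come from one draw; with correlation 0.9 between their errors, the four-contrast figure is 13.8%. It is 10.6% if the tumor SD is also double the others, but 18.1% if the tumor SD is half the others with no correlation. The combined figures in step 4 hold only at the CV boundary.

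A reader might go further in three ways that the documents do not support:

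- **That the study's error rate is 30%.** 8.4C does not prescribe unadjusted t-tests. A single ANOVA F-test is equally open and holds 5% within 8.4C, although it does not show which tissues differ and leaves the CV test and 8.5 outside.
- **That n=20 is wrong.** It is adequate for the one-sided test described in 8.7. The shortfall arises only if the two-sided rule in 8.6 governs.
- **That the open details of 8.4C (scale, averaging of replicates, missing adipose or normal tissue) are errors of the same kind.** They are choices not yet written down, and they contradict no stated figure.

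**Conclusion.** The point stands: 8.6 describes properties that the plan does not have.

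The firmer part is sidedness. It needs only the inputs in 8.7: about 92% power one-sided (91% with the exact log SD) against about 83% (81%) two-sided.

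The multiplicity part is certain in kind, because no rule delivers an overall 0.05. Its size is conditional on unadjusted paired t-tests, equal matrices and equal, independent errors: about 16% or 30% within 8.4C (9% or 13% for three tissues), and under that model at most about 20% or 33% with the CV test included.

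The consequence is minor to moderate. The main deliverables are concentration estimates, which do not depend on these p-values.

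**What to change.** 1. **8.6:** state that the 0.05 applies to the tumor CV test alone.
2. **8.4:** list that test in the primary analysis plan.
3. **Reconcile 8.6 with 8.7.** Either declare the CV test one-sided at 5%, which keeps the 90% figure, or keep it two-sided and restate power at CV 15% as about 83%, or the minimum detectable CV as about 14.3%. Keeping two-sided testing and 90% power at 15% would need n=24.
4. **8.4C and 8.5:** state that the p-values are nominal and outside the 0.05. Report the tumor-to-other-matrix differences in 8.4C as estimates with 95% confidence intervals.
5. **If inference between matrices is wanted:** apply Holm over the four tumor contrasts and claim control within that family only.

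Splitting the 0.05 over everything is a poor alternative. Over an assumed 13 tests (one CV, ten pairs, two histoscores) each would get 0.05/13 = 0.00385. At that level the one-sided CV test has about 50% power at CV 15% and would need n=36 for 90%.

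**Cost:** a few lines of text, with no new samples or assays. Less may be claimed from the 8.4C and 8.5 p-values, and the stated power falls if two-sided is kept. The nominal label has no power cost. Holm does: with an assumed within-patient log SD of 0.4 and a 1.5-fold tumor-to-plasma ratio, power falls from 86% to 78% if tumor differs from all four matrices, or to 67% if only plasma differs. At 2-fold it stays at 99% or higher.

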1.2. Metformin Pharmacokinetics

While metformin is generally well-tolerated by patients, the anti-hyperglycemic response between patients is quite variable. With a twice-daily (BID) oral dose of 750 mg, metformin has a plasma elimination half-life of approximately 6 h. Absorption of the tablet occurs predominately in the small intestine, and is mediated through plasma membrane monoamine transporters (PMATs). However, this absorption is often incomplete, resulting in substantial inter-patient variation in drug bioavailability. Mean drug bioavailability is 55% +/- 16%. Because of this, there is large inter-individual variability in metformin pharmacokinetics (11). Steady-state metformin plasma concentrations can range from 54 to 4133 ng/mL (12). While no accumulation in plasma has been seen in patients after multiple doses, metformin elimination is bi-phasic. While initial elimination of metformin from plasma is relatively rapid, there is a second more prolonged elimination phase possibly due to slow uptake and release from a secondary compartment in tissues (11, 13). Metformin exists as a hydrophilic cationic species at physiologic pH, and as such, has severely limited passive diffusion through tissues. Despite this, metformin is still widely distributed throughout the body and is transported to the liver and other peripheral tissues mainly through organic cation transporters 1 and 3 (OCT1/3) (14). Metformin is not metabolized, is poorly plasma protein-bound and is eliminated from the body by renal excretion into the urine (15).

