2.0 OBJECTIVES

2.1 Primary Objective

To determine the intra-tumor concentrations of metformin, with a standard deviation $\leq 25\%$ of the mean, in patients with solid tumors of thoracic origin administered metformin extended release.

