Metformin (1, 1-Dimethylbiguanide hydrochloride) is a synthetic biguanide derivative. Administered orally, this drug is predominately used to help lower blood glucose concentrations in diabetes mellitus type 2 patients. Metformin effectively lowers blood glucose concentrations in patients by decreasing hepatic glucose output, and increase peripheral glucose uptake and utilization (3, 4). Metformin also decreases circulating insulin and fatty acid concentrations in patients (8).

Preclinical and pharmacodynamic data in humans

Oral metformin is absorbed in the small intestinal tract and taken up through plasma membrane monoamine transporters (PMATs). Metformin is predominantly transported into cells via organic cation transporters (OCT1/3). Metformin has a plasma half-life of 5-6 h (11). Due to inter-patient variability in drug absorption and transport, steady-state metformin plasma concentrations can range from 0.054 to 4.133 ug/mL (0.08- 6.21 uM) (15). Estimated therapeutic concentrations of metformin range from 0.129 to 90 ug/mL (0.19 uM to 132.9 uM) (33).

Selectivity of metformin

Metformin is canonically an agonist of AMPK; however it has also been reported to weakly inhibit mitochondrial respiratory complex 1 *in vitro* (5, 7). In diabetics, metformin systemically lowers blood glucose concentrations by inhibiting hepatic

glucose output and increasing glucose utilization, without causing hyperinsulinemia, hypoglycemia, or promoting weight gain (3). Metformin also systemically increases insulin sensitivity and decreases concentrations of circulating fatty acids (6).

Toxicities and risks of metformin

In worldwide placebo-controlled clinical trials, 781 patients with type 2 diabetes were administered metformin extended release (Glucophage® XR; 500 or 750 mg), and 195 patients received placebo. Adverse reactions reported in >5% of the metformin extended release-treated patients, and that were more common in metformin extended release-treated than placebo-treated patients, are noted in the table below [extracted from Glucophage® product insert (34)].

Adverse Reaction	GLUCOPHAGE XR (n=781)	Placebo (n=195)
	% of Patients	
Diarrhea	9.6	2.6
Nausea/Vomiting	6.5	1.5

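### The 25% SD/mean target in the Primary Objective and Section 8.7 is not derived anywhere, fits poorly with the plasma variability that 8.7 adopts as surrogate, and rests on a one-sided test absent from 8.4 and contrary to 8.6

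*Combined protocol and SAP*

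**What the plan says.** Section 2.1 states the Primary Objective as "To determine the intra-tumor concentrations of metformin, with a standard deviation" of no more than 25% of the mean.

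Section 8.7 proposes 20 evaluable patients "to account for the wide range (>75-fold) of steady-state plasma concentrations of metformin previously shown in" humans. It says that no intra-tumor data exist and takes plasma as the surrogate, "under the assumption that plasma and tumors will exhibit similar ranges of variability between patients". Section 1.2 gives the range: "Steady-state metformin plasma concentrations can range from 54 to 4133 ng/mL". Section 4.2.3 repeats it and explains it: "Due to inter-patient variability in drug absorption and transport, steady-state metformin plasma concentrations can range from 0.054 to 4.133 ug/mL".

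For the calculation, 8.7 says: "The log chi-square test is used to find the minimum detectable coefficient of variation". On scale, "we use the fact that the CV is approximately equal to SD on the log scale". The calculation is one-sided with n=20 and a null CV of 25%, and gives a minimum detectable CV of 15% "with 90% power and the Type I error alpha=5"%.

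Section 8.4 plans descriptive statistics for variability between patients and names no test of a CV against 25%. Section 8.6 makes every test two-sided with an overall type I error of 0.05.

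**The concern.** The same section holds two statements about spread that are hard to reconcile. One says that tumor concentrations should vary between patients about as much as plasma concentrations, which span more than 75-fold. The other treats a CV of 25% as the value to be beaten. No plasma CV or SD is given, and no passage connects the 25% to the plasma data.

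Two things are at stake. The Primary Objective carries a numerical condition that the study may well miss even if it measures concentrations accurately. And the only statement of what 20 patients deliver is the power of a test that the analysis plan does not contain, so the reader is not told how precisely the concentrations will be estimated.

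**Working it through.** **Inputs.** n=20, null CV 25%, one-sided 5%, detectable CV 15%, power 90%, CV taken as log SD (8.7). Plasma range 54 to 4133 ng/mL and bioavailability 55% +/- 16% (1.2). Two-sided 0.05 (8.6).

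**1. The plan's own figure.** The test rejects when 19·s²/0.25² falls below χ²(0.05; 19) = 10.117, that is, when the observed log SD is at most 0.25·√(10.117/19) = 0.182.
- Power at CV 15%: P(χ²₁₉ < 10.117·(0.25/0.15)²) = P(χ²₁₉ < 28.10) = 0.919.
- Detectable CV at 90% power: 0.25·√(10.117/27.204) = 0.152.

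The stated 15% is reproduced.

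**2. The same test under 8.6.** With 0.025 in the lower tail, χ²(0.025; 19) = 8.907.
- Power at CV 15%: P(χ²₁₉ < 24.74) = 0.831.
- Detectable CV at 90% power: 0.25·√(8.907/27.204) = 0.143.

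**3. The plasma range against 25%.** 4133/54 = 76.5 and ln(76.5) = 4.34. At log SD 0.25 the range is 4.34/0.25 = 17.4 SDs wide. For comparison, log-normal data with a CV of 25% have an expected max/min ratio of about 2.5 in 20 patients and 6.7 in 10,000.

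**4. Chance of meeting the criterion.** A range does not determine an SD, and the source's size, doses and distribution are not in the documents. The true log SD, s, is therefore an assumption. Two events matter:
- the one-sided 5% test rejects: P(χ²₁₉ < 10.117·(0.25/s)²);
- the observed log SD is at most 0.25, the descriptive reading of 2.1: P(χ²₁₉ ≤ 19·(0.25/s)²).

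| Assumed log SD | Where it comes from | Test rejects | Observed log SD ≤ 0.25 |
|---|---|---|---|
| 0.15 | detectable value in 8.7 | 92% | >99.9% |
| 0.20 | between the two values in 8.7 | 33% | 94% |
| 0.25 | null in 8.7 | 5% | 54% |
| 0.29 | 16/55, if 16 is an SD in percentage points | 0.9% | 22% |
| 0.361 | range spans 12 SDs (4.34/12) | 0.05% | 2.8% |
| 0.50 | range spans 8.7 SDs (4.34/0.50) | about 0 | 0.04% |

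**5. What n=20 does deliver.**
- The 95% CI for the log SD runs from √(19/32.852) = 0.76 to √(19/8.907) = 1.46 times the estimate.
- The 95% CI factor for the geometric mean is exp(2.093·s/√20): 1.12, 1.21, 1.32, 1.45 and 1.60 for s = 0.25, 0.4, 0.6, 0.8 and 1.0.

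**The case against.** The strongest reply has four parts.

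- **The power statement is accurate.** Section 8.7 calls 15% the minimum detectable CV and never calls it the expected one. Any power figure holds only at its alternative or beyond. This stands: a reader might infer that the calculation is wrong or that 15% is presented as a forecast, and the documents support neither.
- **The range does not fix the CV.** A reader might infer that a 76-fold range proves a particular large tumor CV, or rules out 25%. It does not. With no distribution assumed, a sample holding both extremes can have log SD 0.25 or less if it has at least 1 + 4.338²/(2·0.0625) = 151.5, so 152, subjects with all the others at the log midpoint. That arrangement is extreme, but it is not excluded.
- **Spread here could be smaller than in the source.** Study-treated patients share one regimen and a timed last dose, and eligibility requires eGFR or eCrCL above 60. The bioavailability figure, if its 16 is an SD, suggests about 29%, much nearer 25%. This stands too, but bioavailability is only one component of exposure, and at 29% the test still almost never rejects. Spread could also be larger: Section 3.3 admits existing users on any dose, and 3.1 admits several tumor sites.
- **Little depends on it.** Section 8.1 defines the endpoint as concentrations, 8.4 reports their variability descriptively, and no success or stopping rule uses 25%. This limits the harm, but it does not explain why 25% stands in the Primary Objective with a powered test behind it.

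**Conclusion.** The point holds. The 25% criterion is not derived from anything in the plan, and it sits badly with the variability that 8.7 adopts for tumor. The test that supports the sample size is missing from 8.4, and its one-sided form conflicts with 8.6; under 8.6 the power at CV 15% is 83% rather than about 90%. These statements rest on the text and on arithmetic alone.

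How unlikely the criterion is to be met depends on the assumed tumor log SD and on a log-normal model. From 0.29 to 0.5, the chance that the test rejects goes from 0.9% to about zero, and the chance that the observed log SD is at most 0.25 goes from 22% to 0.04%. So the criterion is unlikely to be met under the plan's own surrogate, but not shown to be impossible. A reader might also infer that the trial would then have failed. The documents do not support that, because no decision is tied to 25% and the concentrations would be reported in any case. This should be fixed, but it does not threaten the study's main measurements.

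**What to change.** In 2.1, 8.4 and 8.7, define the primary result as the tumor concentration (for example the geometric mean) and its between-patient CV, each with a 95% confidence interval. Remove the 25%, or label it a descriptive benchmark.

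In 8.7, replace the 90% power sentence with the precision at n=20: a 95% CI for the log SD from 0.76 to 1.46 times the estimate, and a geometric mean known to within a factor of 1.12, 1.21, 1.32, 1.45 or 1.60 for an assumed log SD of 0.25, 0.4, 0.6, 0.8 or 1.0.

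If the test is kept, justify the 25% null against the plasma surrogate and add the test to 8.4. Then either declare it a one-sided exception to 8.6, or restate the power as 83% at CV 15% (detectable CV 14.3% at 90% power).

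The cost is wording in three sections and the calculation of confidence intervals, with no extra patients or samples. The drawback is that the stated precision looks less favourable than 90% power.
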